11.2.2. Evaluating Adverse Events

11.2.2.1. Intensity/Severity Grade

The **intensity** of each AE will be graded using National Cancer Institute (NCI) Common Terminology Criteria for Adverse Events (CTCAE) v 4.03. The criteria can be accessed at: https://ctep.cancer.gov/protocolDevelopment/electronic_applications/docs/CTCAE_v5_Quick_Reference_5x7.pdf.

It is important to distinguish between serious and severe AEs. Severity is a measure of intensity whereas seriousness is defined by the criteria under Section 11.2.1.3. An AE of severe intensity may not be considered serious.

Grade refers to the intensity of the AE. The CTCAE displays Grades 1 through 5 with unique clinical descriptions of intensity for each AE based on this general guideline:

Table 8: CTCAE Intensity Grades

| Grade | Description |
|----------------|---|
| Grade 1 | Mild; asymptomatic or mild symptoms; clinical or diagnostic observations only; intervention not indicated |

Table 8: CTCAE Intensity Grades (Continued)

| | |
|----------------|---|
| Grade 2 | Moderate; minimal, local, or noninvasive intervention indicated; limiting age-appropriate instrumental activities of daily living (ADL) |
| Grade 3 | Severe or medically significant but not immediately life-threatening; hospitalization or prolongation of the hospitalization indicated; disabling; limiting self-care ADL |
| Grade 4 | Life-threatening consequences; urgent intervention indicated |
| Grade 5 | Death related to AE |

11.2.2.2. Assessment of Causality

The Investigator is responsible for making an assessment of the causal relationship between the AE and the study drug, SCS Microinjector, and/or study procedure based on the available information.

The causal relationship of the AE is assessed using a binary system, and AEs are classified as either Related or Unrelated to the study drug, SCS Microinjector, and/or study procedure.

In assessing this relationship, the Investigator should consider the potential etiologies for the observed AE. An AE may be related to:

- The study drug(s).
- Other concomitant medications.
- Underlying disease pathology.
- A pre-treatment condition.
- A procedure performed in the course of the study.
- Other alternative reason.

Among the potential etiologies, the Investigator should make a determination based on the most likely causal relationship. The causality assessment provided for an AE or SAE should be accompanied by all available supporting evidence, including but not limited to supporting laboratory tests, histopathology, history of the presenting event, medical history, temporal association, and results of relevant diagnostic procedures.

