10. STUDY DRUG MATERIALS AND MANAGEMENT

This is an open-label, non-interventional extension of the Parent study, CLS1002-101. No study drug will be dispensed or administered to the subjects as part of this protocol. Additional treatments administered during this study will be recorded as concomitant and/or rescue medications. Storage of permitted additional treatments should be according to the Prescribing Information for the individual treatment(s) and is the responsibility of the Investigator.

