11.2.4. Reporting Adverse Events

All AEs (related and unrelated) will be recorded from the signing of consent form until 30 days after the end of study participation. All SAEs occurring during subject participation, and all SAEs considered related to the study drug, SCS Microinjector, and/or study procedure and discovered by the Investigator at any time after the study should be reported. All such SAEs must be reported to Clearside Biomedical, or its designee, within one 24 hours of the knowledge of the occurrence of the event. The Investigator must complete, sign and date the SAE pages, verify the accuracy of the information recorded on the SAE pages with the corresponding source documents, and send a copy by email ([contact]) to Clearside Biomedical, or its designee.

Additional follow-up information, if required or available, should all be emailed or faxed to Clearside Biomedical, or its designee, within one business day of receipt. This information should be recorded on a follow-up SAE form and placed with the original SAE information and kept with the appropriate section of the CRF and/or study file.

Clearside Biomedical and/or its designee is responsible for notifying the relevant regulatory authorities of certain events. It is the Principal Investigator's responsibility to notify and submit required safety information to their IRB or IEC. This information includes, but is not limited to, any safety alert letter received from the Sponsor and any SAEs occurring at their investigative site.

Investigators will also be notified of all unexpected, serious, drug-related events, SCS Microinjector related events and study procedure related events (7/15 Day Safety Reports) that occur during the clinical trial. Each site is responsible for notifying its IRB or IEC of these additional SAEs. A copy of these reports must be retained at the investigative site and file in the Trial Master File.

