11.2.5. Follow-up of AEs and SAEs

All AEs and SAEs reported during study conduct must be followed until resolution, or until the Investigator assesses them as stable or chronic, the subject withdraws consent, or the subject is lost to follow-up. Subjects will be followed for any treatment-related, SCS Microinjector related,

and/or study procedure related SAEs reported at the end of participation until the condition stabilizes, the event is otherwise explained, the subject is lost to follow-up, the subject withdraws consent, or the subject experiences a fatal outcome.

NOTE: “Resolution” means the subject has returned to baseline state of health, or the Investigator does not expect any further improvement in the subject’s condition or does not expect worsening of the AE.

For a non-serious AE that is first identified on the last scheduled contact, the event must be recorded on the AE CRF with the current status noted, but no further follow-up needs to be performed unless deemed necessary by the Investigator or the Sponsor.

Post-Study SAEs: Investigators are not obligated to actively seek SAE information in former study participants; however, any new SAE reported by the subject to the Investigator that occurs after the last scheduled contact and is determined by the Investigator to be associated with the use of study drug, the use of the SCS Microinjector, and/or study procedure, should be reported to the Sponsor. The Investigator should follow related SAEs identified after the last scheduled contact until the event has resolved or stabilized or the subject is lost to follow-up.

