12.5.2. Safety Analysis

The summary of adverse events (and SAEs) will be limited to TEAEs. Treatment-emergent adverse events are defined as an event that emerges during treatment with CLS-AX (Visit 2, Day 1) having been absent pre-treatment or worsens relative to the pre-treatment state.

For summarizing adverse events, each reported adverse event term will be coded to a preferred term and its corresponding system organ class (SOC) using the Medical Dictionary for Regulatory Activities (MedDRA) coding dictionary. Summary tables will be presented by dose cohort.

Summary tables of TEAEs will be produced for the following categories divided into Study Eye TEAEs, Fellow Eye TEAEs, ocular TEAEs, non-ocular TEAEs and overall TEAEs, grouped by SOC and preferred term:

- All TEAEs.
- All treatment-related TEAEs.
- All TEAEs leading to study discontinuation.
- All SAEs.
- All treatment-related SAEs.
- All TEAEs leading to death.

For each summary, adverse events will be summarized by presenting the number and percentage of subjects reporting each event at least once, and the total number of events reported.

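### Causality is decided by the single most likely cause, so an event that CLS-AX may have contributed to can be coded Unrelated and left out of the related-event summaries

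*Combined protocol and SAP*

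**What the plan says.** Section 11.2.2.2 makes the investigator responsible for causality on a binary scale: "AEs are classified as either Related or Unrelated to the study drug, SCS Microinjector, and/or study procedure". It lists causes to consider: study drug, "Other concomitant medications", "Underlying disease pathology", a condition present before treatment, a procedure done during the study, and other reasons. The choice is then made as follows: "Among the potential etiologies, the Investigator should make a determination based on the most likely causal relationship". There is no intermediate category, and no other section supplies a threshold.

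Section 10 places anti-VEGF treatment given during follow-up among the rival causes: "Additional treatments administered during this study will be recorded as concomitant and/or rescue medications".

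The coding is used in several places:

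- The Synopsis (Criteria for evaluation) groups the primary safety outcome by relatedness, among other things.
- Section 12.5.2 plans tables of "All treatment-related TEAEs" and of treatment-related SAEs.
- Section 11.2.5 asks for a new SAE after the last scheduled contact to be reported if it "is determined by the Investigator to be associated with the use of study drug, the use of the SCS Microinjector, and/or study procedure". Sections 11.2.3 and 11.2.4 apply a similar filter.
- Section 11.2.4 adds: "Investigators will also be notified of all unexpected, serious, drug-related events", with device-related and procedure-related events alongside.

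Sections 12.4.1 and 12.5 say that safety summaries use Parent and extension data together.

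**The concern.** Under this rule Related means that a study cause beat every rival, not that it plausibly played a part. Here a rival is always to hand. Every subject has nAMD, and subjects who receive additional anti-VEGF therapy stay in follow-up to Visit 8 (Section 9.4.1). Section 5 reports that only 2 of 6 Cohort 1 subjects completed the Parent study without meeting the additional therapy criteria, so the second rival may be common too.

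The study is small and has no control arm that could reveal an excess of events put down to disease. Its primary objective is safety. A summary of related events that leans toward zero for disease-like ocular events could be read as reassurance that the data do not give.

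**Working it through.** The plan states no figure on this point, so there is none to reproduce. The check traces the rule to its outputs and then illustrates the size.

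**1. What the rule does.** Suppose the investigator's beliefs about the candidate causes sum to 1, and let p be the share given to CLS-AX.

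- Two candidates: CLS-AX is chosen only if p > 1/2. Anything below 50% is Unrelated.
- Three candidates: if p < 1/3, the other two share more than 2/3, so at least one exceeds 1/3 and CLS-AX must lose. Between 1/3 and 1/2 the result depends on how the rest is split: CLS-AX can lose just under 50% and can win at 34%.

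So the rule has no fixed bar; it moves with the number of rivals considered. Investigators do not assign such probabilities. The arithmetic only shows what the sentence implies.

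**2. Direction.** Compare with a rule that codes Related whenever a study cause is a reasonable possibility. An event for which a study cause is likeliest would ordinarily be Related under both. An event for which it is plausible but second is Related only under the possibility rule. The present rule can therefore only lower the related count by comparison.

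**3. Which outputs depend on the coding.**

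| Output | Section | Depends on the Related/Unrelated call? |
|---|---|---|
| Number of subjects with TEAEs and SAEs | 7.2.1 | No |
| All-TEAE and all-SAE tables | 12.5.2 | No |
| Recording of AEs to 30 days after participation | 11.2.3, 11.2.4 | No |
| Reporting of on-study SAEs | 11.2.4 | No |
| Relatedness grouping of the primary criterion | Synopsis | Yes |
| Treatment-related TEAE and SAE tables | 12.5.2 | Yes |
| Reporting of new SAEs after the study | 11.2.3 to 11.2.5 | Yes |
| 7/15-day notices to investigators | 11.2.4 | Not determinable: the text does not say whose causality call applies |

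For post-study SAEs the loss is clearest beyond 30 days after participation, when the general AE recording window has closed. Section 11.2.5 adds that investigators need not look for such events.

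**4. Size, for illustration.** Inputs: about 5 subjects per cohort and a maximum of 19 (Section 12.2). Exact 95% limits are the Clopper-Pearson limits: lower = the 0.025 quantile of Beta(x, n − x + 1), upper = the 0.975 quantile of Beta(x + 1, n − x).

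| Subjects with a related event | Rate | 95% interval |
|---|---|---|
| 1 of 5 | 20% | 0.5% to 71.6% |
| 0 of 5 | 0% | 0% to 52.2% |
| 1 of 19 | 5.3% | 0.1% to 26.0% |
| 0 of 19 | 0% | 0% to 17.6% |

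If a subject's only related event is recoded, the cohort rate falls by 20 percentage points (1/5 − 0/5).

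**5. What a zero could hide.** Assumption, not in the documents: three independent events, each with probability p of being due to CLS-AX and each with one likelier rival, with p from 20% to 45%. All three are coded Unrelated. The chance that at least one is drug-caused is 1 − (1 − p)³: 1 − 0.80³ = 49% at p = 20%, and 1 − 0.55³ = 83% at p = 45%.

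**The case against.** The strongest reply is that safety capture is largely protected and that a stricter threshold is a legitimate sponsor choice. Much of this stands.

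- **A reader might infer that such events vanish.** They do not. They stay in the all-cause endpoint and tables, and on-study SAEs reach the sponsor within 24 hours whatever their cause. BCVA, IOP and imaging are summarised by cohort without reference to causality (Section 12.5.3).
- **A reader might infer that the rule blocks the 7/15-day notices.** The documents do not support this. The sponsor holds every on-study SAE, and Section 11.2.4 does not say whose judgement defines drug-related.
- **A reader might infer that a late fall in vision would be coded Unrelated.** It could be, but the investigator may judge CLS-AX likelier. Sections 11.2.1.1 and 11.2.1.2 also act earlier: a change judged to be expected progression is not an AE and never reaches the causality step. The fix does not touch that.
- **Additional therapy may not always be a rival.** An investigator might treat the injection as a procedure performed in the study and code the event Related to study procedure. The documents do not settle this, nor whether treatment-related in Section 12.5.2 covers device and procedure. The rival that is certain is nAMD.
- **The missing Microinjector entry is minor.** The two sentences before the list already require a judgement on the device, and the list has an open last item.
- **The study should not be called first-in-human.** The documents say a Phase 1/2a dose-escalation Parent study, and no investigational product is given in the extension.
- **Changing the rule here alone could mix two definitions of Related in one pooled table.** This is a fair point, and the fix has to deal with it.

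None of this supplies a possibility threshold, or removes the downward lean in the related-event summaries or the filter on new post-study SAEs.

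**Conclusion.** The point holds within limits. As written, Section 11.2.2.2 lets a plausible contribution from CLS-AX, the SCS Microinjector or the study procedure be coded Unrelated because another cause ranks higher. Compared with a possibility standard, this biases downward the relatedness grouping of the primary criterion and the two treatment-related tables, and it lets a new SAE after the study go unreported.

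The conclusion rests on investigators following the sentence as written. The 20-point shift is simply one subject in five, and the 49% to 83% range depends on assumed probabilities. The number of events affected cannot be derived from the documents. A claim that the trial would miss drug toxicity altogether is not supported. This is a change that should be made, not a flaw that invalidates the primary endpoint.

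**What to change.** Replace the most-likely-cause sentence in Section 11.2.2.2 with: *Classify as Related if there is a reasonable possibility that the study drug, SCS Microinjector or study procedure caused or contributed to the event, even if another cause is also plausible or more likely; otherwise Unrelated.* Record the alternative cause as free text on the CRF.

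Because the tables pool both studies, confirm which causality rule the Parent study used; the documents do not show it. If it differs, present related events separately by study of onset.

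Adding the SCS Microinjector to the list of causes is a minor clarification that can go in at the same time.

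The cost is one sentence, one list item, one free-text field and CRF completion guidance, plus a split table if the two rules differ. The downside is that more events will be labelled Related, some of them because of disease, and some additional reports will be sent. The all-cause tables remain available to put those counts in context.

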11.2.3. Recording Adverse Events

Adverse events spontaneously reported by the subject and/or in response to an open question from the study personnel or revealed by observation will be recorded during the study at the investigational site on the CRF. Information about AEs will be collected from the time of signing of the consent form until 30 days after the end of study participation. Detailed information regarding all SAEs should be collected from the signing of the informed consent until the end of the study. SAEs that are considered related to the use of study drug, SCS

Microinjector, and/or study procedure by the Investigator may be reported by the Investigator if they occur after the end of the study. The Investigator must continue to follow the patient until the SAE has resolved, the condition has become chronic in nature, the condition stabilizes (in the case of persistent impairment), the patient experiences a fatal outcome or is lost to follow up.

The AE term should be reported in standard medical terminology as concisely as possible. In general, the AE recorded should not be a procedure, outcome, or clinical/laboratory measurement, but should reflect the event leading to the procedure, outcome, or the cause of the clinical/laboratory abnormality, if known. Whenever possible, AEs should be evaluated and recorded as a diagnosis, rather than as individual signs or symptoms. However, if a definitive diagnosis is not possible, the individual signs and symptoms should be recorded. For each AE, the Investigator will evaluate and report the onset (date and time), resolution (date and time), intensity, causality, action taken, seriousness, outcome (if applicable), and whether or not it caused the patient to discontinue the study.

11.2.4. Reporting Adverse Events

All AEs (related and unrelated) will be recorded from the signing of consent form until 30 days after the end of study participation. All SAEs occurring during subject participation, and all SAEs considered related to the study drug, SCS Microinjector, and/or study procedure and discovered by the Investigator at any time after the study should be reported. All such SAEs must be reported to Clearside Biomedical, or its designee, within one 24 hours of the knowledge of the occurrence of the event. The Investigator must complete, sign and date the SAE pages, verify the accuracy of the information recorded on the SAE pages with the corresponding source documents, and send a copy by email ([contact]) to Clearside Biomedical, or its designee.

Additional follow-up information, if required or available, should all be emailed or faxed to Clearside Biomedical, or its designee, within one business day of receipt. This information should be recorded on a follow-up SAE form and placed with the original SAE information and kept with the appropriate section of the CRF and/or study file.

Clearside Biomedical and/or its designee is responsible for notifying the relevant regulatory authorities of certain events. It is the Principal Investigator's responsibility to notify and submit required safety information to their IRB or IEC. This information includes, but is not limited to, any safety alert letter received from the Sponsor and any SAEs occurring at their investigative site.

Investigators will also be notified of all unexpected, serious, drug-related events, SCS Microinjector related events and study procedure related events (7/15 Day Safety Reports) that occur during the clinical trial. Each site is responsible for notifying its IRB or IEC of these additional SAEs. A copy of these reports must be retained at the investigative site and file in the Trial Master File.

11.2.5. Follow-up of AEs and SAEs

All AEs and SAEs reported during study conduct must be followed until resolution, or until the Investigator assesses them as stable or chronic, the subject withdraws consent, or the subject is lost to follow-up. Subjects will be followed for any treatment-related, SCS Microinjector related,

and/or study procedure related SAEs reported at the end of participation until the condition stabilizes, the event is otherwise explained, the subject is lost to follow-up, the subject withdraws consent, or the subject experiences a fatal outcome.

NOTE: “Resolution” means the subject has returned to baseline state of health, or the Investigator does not expect any further improvement in the subject’s condition or does not expect worsening of the AE.

For a non-serious AE that is first identified on the last scheduled contact, the event must be recorded on the AE CRF with the current status noted, but no further follow-up needs to be performed unless deemed necessary by the Investigator or the Sponsor.

Post-Study SAEs: Investigators are not obligated to actively seek SAE information in former study participants; however, any new SAE reported by the subject to the Investigator that occurs after the last scheduled contact and is determined by the Investigator to be associated with the use of study drug, the use of the SCS Microinjector, and/or study procedure, should be reported to the Sponsor. The Investigator should follow related SAEs identified after the last scheduled contact until the event has resolved or stabilized or the subject is lost to follow-up.

11.2.6. Exposure *in utero* During Clinical Trials

The Sponsor must be notified of any patient who becomes pregnant while participating in the clinical trial. Although pregnancy is not considered an AE, all pregnancies must be followed to conclusion to determine their outcome. This information is important for both drug safety and public health concerns. It is the responsibility of the Investigator or designee to report any pregnancy in a subject that occurs during the study. Should a patient in the study become pregnant, the site must complete the Exposure *in utero* reporting form. Notification should be made within 24 hours of awareness of the event.

It is the responsibility of the Investigator, or designee, to report any pregnancy and the anticipated date of birth that occurs while receiving, or within 30 days of discontinuing the study drug, via the Exposure *in utero* reporting form. If the pregnancy is to be terminated, the anticipated date of termination should be provided.

If it is the partner, rather than the subject, who is found to be pregnant, after obtaining the partner’s consent, the Exposure *in utero* reporting form should be completed with the anticipated date of birth/termination and details regarding the partner should be entered in the narrative section of the form.

The patient/partner should be followed by the Investigator until completion of the pregnancy. If the pregnancy ends for any reason before the anticipated date of birth/termination, the Investigator should notify the Sponsor. At the completion of the pregnancy, the Investigator will document the outcome of the pregnancy. If the outcome of the pregnancy meets criteria for immediate classification as an SAE (i.e., post-partum complications, spontaneous abortion, miscarriage, still birth, neonatal death, or congenital anomaly (even of an aborted fetus), the Investigator should follow the procedures for reporting an SAE. Note, elective termination of a pregnancy would not meet criteria as an SAE and in these cases a follow up pregnancy report should be provided by the Investigator.

